In patients undergoing neurosurgical procedures, intraoperative blood loss is a very common problem that anesthesiologists encounter. Bleeding can result from dilated epidural venous plexus, soft tissue paraspinal blood vessels, tumor hypervascularity, and even uninvolved bone. [1] This massive amount of blood loss may lead to perioperative coagulopathy, and therefore use of allogeneic blood products such as: blood, platelets, and/or coagulation factors.[2] However, blood product transfusions are associated with significant complications that also need to be taken into consideration when thinking about transfusions; these involve, but are not limited to: infections, acute lung injury, organ dysfunction, and multiorgan failure. Therefore, an early and specific characterization of the cause of bleeding is crucial to achieve an effective and goal directed perioperative hemostatic therapy and reduce these types of complications. [3, 4]

The estimated blood loss is different between surgical procedures; in spinal fusion surgeries it has been documented to be between 650 to 2839 mL per patient, with transfusion requirements in 50% to 80% of the patients analyzed. [2] Patients undergoing surgical procedures for scoliosis had an estimated blood loss of 975.4 \pm 318.7 mL [5]; and in spine metastatic disease, a meta-analysis performed by Chen et al. showed blood loss ranges between 1100 ml to 6039 ml, with blood losses greater than 5000 ml present in 12% of the patients. [6]

This amount of bleeding warrants massive transfusion for resuscitation and requires an adequate hemostatic approach in order to prevent massive hemorrhage complications such as acidosis, hypothermia, and coagulopathy. In addition, it can also lead to surgical complications, such as incomplete spinal decompression, inadequate spinal fixation, poor neurologic outcomes, or death. [1]

Coagulopathy and/or uncontrolled bleeding are caused by defects on clot stability and firmness. Deficiency of coagulation factors, fibrinogen, and platelets lead to defects on clot firmness, while hyperfibrinolysis and factor XIII deficiency lead to decrease clot stability. Several studies have underscored the importance of avoiding acidosis, hypothermia, and coagulopathy; these studies have been performed mainly in cardiac surgery and trauma populations. [7]

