- Compare the amount of Cryoprecipitate and Platelets transfused intraoperative between both groups.
- Compare the amount of all blood products transfused at 6, 12, and 24 hours postoperative.
- Compare the incidence and requirements of fibrinogen concentrate, PCC, antithrombin concentrate, factor XIII concentrate, and activated recombinant factor VII, or any other hemostatic therapy. Compare variables that affect coagulopathy such as acidosis and hypothermia.
- Compare hemodynamic variables (BP, HR, O2, Temperature, Arterial blood gases) during surgery.
- Compare postoperative time of mechanical ventilation
- Compare length of ICU stay and overall hospital stay
- Compare total in hospital need for transfusion
- Compare postoperative coagulation status on days 1 and 3 if available
- Compare overall infection rate
- Compare 30 days mortality

3. Exploratory objectives

Compare the total costs of intra-operative blood transfusion guided with ROTEM versus laboratory coagulation tests in patients undergoing major spinal surgeries.

III. Material and methods

1. Study design:

This is a prospective, randomized parallel-group, single center study in patients undergoing elective major spine surgery. Patients will be randomized to guide blood transfusion administration with ROTEM or laboratory coagulation tests (ABG, PT, PTT, aPTT, Hb, platelets,

Version: 1.0

and fibrinogen). Randomization list will be computer-generated using a balanced allocation ratio 1:1.

- 2. Inclusion and exclusion criteria:
- Inclusion criteria
- 1. Male or female age 18 years or older.
- 2. Able to provide inform consent.
- 3. Patients schedule to undergo elective major spinal, orthopedic, or combined procedures under general anesthesia that are expected to receive intraoperative blood products and last greater than 2 hours.
- Exclusion criteria
 - 1. Subjects younger than 18 years old.
 - 2. Subjects who are prisoners.
 - 3. Subjects who refuse transfusion of blood products.
 - 4. Subjects unable to participate in the study for any reason in the opinion of the Principal Investigator.
 - 5. Subject with past medical history of uncontrolled coagulopathies.

3. Study population and sample size:

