The power analysis has been calculated based on a mean estimated RBC transfusion of 8 units with a conservatively estimated standard deviation of 5. We expect that ROTEM will decrease the RBC transfusion by 3 units. We make the same assumptions for FFP. We will test each main outcome between the ROTEM and control groups at an alpha of 0.025 (adjusted for 2 main outcomes). We need 110 patients; 55 patients in each group to achieve 80% power to detect a difference of 3 units assuming a standard deviation of 5 at an alpha of 0.025.[3,13]

4. Randomization and study procedures:

Patients will be randomized in a 1:1 ratio to either laboratory coagulation tests or ROTEM. No changes in surgery or anesthesia technique will be made for study's purposes.

a. Laboratory Coagulation Tests

If the patient is randomized to laboratory coagulation tests, anesthesia care providers will assess the hemostatic status according to OSUWMC standard practices and their own clinical criteria.

Laboratory coagulation tests include but are not limited to the following: hemoglobin, platelet count, fibrinogen concentration, INR, aPTT, and PT. These assessments will be performed at fixed perioperative time points (preoperatively, every 2 hours intraoperatively, end of surgery (EOS), and 24 hours after EOS). Intraoperative arterial blood gases will be performed repetitively

Protocol #:2014H0447 Version: 1.0 at a fixed range (every hour) based on anesthesia care provider's decision, along with any other common laboratory tests.

b. ROTEM

If the patient is randomized to ROTEM, the anesthesia care provider will be blinded to any conventional intraoperative coagulation test that might be performed during surgery.

ROTEM will be used according to the manufacturer's instructions using equipment and test reagents provided by Tem International GmbH. All tests will be performed at the bedside by a healthcare provider trained to perform ROTEM. A specific algorithm has been created by [name] (Clinical Director at Tem International GmbH-ROTEM) and should be followed according to measurements obtained during surgery (Figure 1).

ROTEM monitoring will be performed in patients with signs of clinically relevant diffuse bleeding and in whom blood transfusion is considered (Temp >35°C; pH <7.2; Cai >4.6 mg/dL; Hb \ge 9g/dL, or >10g/dL with anticipated greater blood loss) or at a fixed range every 2 hours or at Anesthesiologist criteria based on patient's clinical situation.

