Patient's clinical situation should be consider as the most important component on the transfusion decision-making process. Packed erythrocytes will be transfused to maintain hemoglobin concentrations >9g/dl or >10g/dl in individuals with underlying cardiovascular disease or anticipated greater blood loss. Individual based dynamics (tachycardia, hypotension, sings of ischemia on electrocardiogram, and lactic acidosis) strongly indicating the need for erythrocyte transfusion will be also part of the decision-making transfusion process by the anesthesia care provider.

5. Data collection

The following data points will be recorded in the interventional and control group patients:

- Demographic information (age, sex, height, weight, BMI, race)
- Medical History (including past and current diagnosis, use of chemotherapy or radiation, type of cancer, medications, surgical history)
- Surgical Information (Procedure type/reason for surgery, length of surgery, perioperative medications, ASA physical classification, type of anesthesia)
- Anesthesia record information
- Baseline (pre-operative) and perioperative coagulation lab values (PT, PTT, INR, HTC, HTC, PLT, FIB) (followed for 24 hours postoperatively)
- Perioperative ROTEM values
- Baseline and perioperative hemodynamics (BP, HR, RR, OXYGEN SATURATION, Temperature).
- Intraoperative arterial blood gases
- Intraoperative blood loss (over time)

Protocol #:2014H0447

Version: 1.0

- Transfusion information (type of product, number of transfused units, time administered) intraoperative and 6, 12, and 24 postoperative.
- Use of other hemostatic therapy
- Use of antifibrinolytic agents
- Intraoperative fluid management (type, volume, and frequency)
- Urine output for the first 24 hours.
- Postoperative time of mechanical ventilation
- Length of ICU stay and hospital stay
- Other intraoperative and postoperative complications (including respiratory failure, overall infection rate)
- Inpatient mortality
- Postoperative Day 30 phone call follow-up to assess serious adverse events and mortality.
- Hemostatic therapy cost assessment

IV. Assessment and reporting of Adverse Events and Serious Adverse Events

The occurrence of adverse events (AE) and serious adverse events (SAE) will be recorded from the time of consent until discharge. For each AE, the relationship to the study procedures and monitoring, severity, expectedness, outcome will be determined by the PI and recorded in the study source accordingly

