- The subject requests to be discontinued from the study

- A protocol violation sufficiently serious as to require subject withdrawal

[figure not shown]
- General or specific changes in the subject's condition that render further treatment unreasonable or unsafe within the standards of clinical practice in the judgment of the Principal Investigator or treating physician.

Any subject may leave the study at any time. If a subject decides to stop participating in the study, there will be no penalty. The subject will not lose any benefits to which they are otherwise entitled. Their decision will not affect their future relationship with The Ohio State University.

Protocol #:2014H0447

Version: 1.0

VI.Figure 1. ROTEM Spine Surgery Algorithm

- ¹ Basic conditions:
 - Temp. >35°C; pH >7.2; Cai++ >4.6 mg/dL.
 - $Hb \ge 9 g/dL$.
- ² Antifibrionolytic therapy:
 - Dirkmann et al. Anesth Analg. 2014 (under review)
 - CT_{FIB} > 600 s represents a flat-line in FIBTEM
 - Chapman et al. J Trauma Acute Care Surg. 2013
- ³ Fibrinogen dose calculation:

- A10_{FIB} 9-12 mm: 50 mg/kg fibrinogen
 (2.5 mL/kg fibrinogen conc. or 5 mL/kg cryoprecipitate)
- A10_{FIB} ≤ 8 mm: 75 mg/kg fibrinogen
 (3.75 mL/kg fibrinogen conc. or 7.5 mL/kg cryoprecipitate)
- ⁴ Platelet concentrate (PC) transfusion:
 - A10_{EX} 35-44 mm: 1 pooled or apheresis PC
 - \circ A10_{EX} < 35 mm: 2 pooled or apheresis PC
 - A10_{EX} \leq 25 mm: Platelet conc. + fibrinogen
- ⁵ If Prothrombin-Complex-Concentrate (PCC) is not available:
 - o 10-15 mL/kg FFP or
 - \circ 45-90 µg/kg rFVIIa (if A10_{EX} and A10_{FIB} are ok but FFP is not effective)
- Simultaneous interventions:
 - Maximum three interventions at the same time (In first analysis and severe bleeding)
 - Maximum two interventions at the same time (In second analysis and moderate to severe bleeding)
 - Only one intervention
 (In second or later analysis and mild to moderate bleeding)

Version: 1.0

Protocol #:2014H0447

Version: 1.0

VIII. REFERENCES

- 1. Bilsky, M.H. and J.F. Fraser, *Complication avoidance in vertebral column spine tumors*. Neurosurg Clin N Am, 2006. **17**(3): p. 317-29, vii.
- 2. Elgafy, H., et al., *Blood loss in major spine surgery: are there effective measures to decrease massive hemorrhage in major spine fusion surgery?* Spine (Phila Pa 1976), 2010. **35**(9 Suppl): p. S47-56.

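### No thromboembolic outcome is named and no by-arm comparison of AEs or SAEs is planned, although the ROTEM algorithm notes list PCC, fibrinogen concentrate and rFVIIa

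*Combined protocol and SAP*

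**What the plan says.** **Harms compared or recorded.** The background section gives the harms of blood products as "infections, acute lung injury, organ dysfunction, and multiorgan failure", without claiming that the list is complete. Among the secondary objectives (II.2), the clinical harm outcomes are "Compare overall infection rate" and 30-day mortality, beside ventilation time and ICU and hospital stay. The data list (III.5) adds "Other intraoperative and postoperative complications (including respiratory failure, overall infection rate", an open list. It also has a telephone call on postoperative day 30 for serious adverse events and death. Section IV records AEs and SAEs from consent to discharge.

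**Products.** II.2 also has the objective "Compare the incidence and requirements of fibrinogen concentrate, PCC, antithrombin concentrate, factor XIII concentrate, and activated recombinant factor VII". In the notes to Figure 1, the alternatives headed "If Prothrombin-Complex-Concentrate (PCC) is not available" are FFP or rFVIIa, and fibrinogen concentrate is offered beside cryoprecipitate.

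**Main outcomes.** II.1 makes intraoperative RBC and FFP the primary comparison. III.3 assumes a "mean estimated RBC transfusion of 8 units with a conservatively estimated standard deviation of 5" and states: "We expect that ROTEM will decrease the RBC transfusion by 3 units". The same assumptions are made for FFP, and each outcome is tested "at an alpha of 0.025 (adjusted for 2 main outcomes").

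**The concern.** FFP avoided is scored as benefit on a main outcome. According to the Figure 1 notes, one way to avoid FFP in the ROTEM arm is to give PCC. Likewise, fibrinogen concentrate can stand in for cryoprecipitate, which is a secondary outcome. The plan compares these substitutes only by how often and how much they are used. They are given to promote clotting, so unwanted clotting is the natural harm to look for, and the plan neither names it nor compares it.

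A report that followed the objectives could state that ROTEM guidance reduced FFP and infection and say nothing by arm about thrombosis. Ad hoc AE reporting is a weak substitute. Thrombosis has no definition and no common set of questions. The investigator judges relatedness to the study procedures and monitoring, so a clot after a concentrate could be filed as unrelated to a monitoring device.

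**Working it through.** **1. Where a thrombosis could enter the data**

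| Route | Would it record a thrombosis? | Compared by arm? |
|---|---|---|
| II.2 infection rate | No | Yes |
| II.2 30-day mortality | Only if fatal | Yes |
| II.2 ventilation time, ICU and hospital stay | Only indirectly | Yes |
| III.5 complications | Yes, the list is open, but thrombosis is not named | No objective |
| IV AEs and SAEs to discharge | Yes, if noticed and reported | No objective |
| III.5 day-30 call | Yes, if serious | Deaths only |

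A pulmonary embolism, stroke or myocardial infarction would ordinarily meet the SAE definition in IV, so serious events have a route into the data. A non-serious thrombosis after discharge has none. No row gives a definition, a common method of ascertainment and a planned comparison together.

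**2. The plan's own sample size**

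Inputs from III.3: difference 3, SD 5, alpha 0.025 per outcome, power 80%.

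- Normal approximation, two-sided: n = 2(2.241 + 0.842)² × 25/9 = 52.8, so 53 per arm.
- Two-sided t-test: 54.08, so 55 per arm and 110 in total, matching the plan. Power at 55 per arm is 80.7%.
- One-sided versions give 44 (normal) or 45 (t), so the stated alpha is evidently two-sided.

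The figure reproduces, and the present point does not depend on it.

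**3. What 55 per arm can say about thrombosis**

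If no event is seen in 55 patients, the exact upper limits are:

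- one-sided 95%: 1 − 0.05^(1/55) = 5.3% (rule of three: 3/55 = 5.5%);
- two-sided 95%: 1 − 0.025^(1/55) = 6.5%.

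The documents give no event rates, so the rates below are assumptions chosen to show a range. Power by normal approximation at two-sided 0.05 is Φ{(|p₂ − p₁| − 1.96√[2p̄(1 − p̄)/55]) / √[(p₁(1 − p₁) + p₂(1 − p₂))/55]}. For 1% vs 3% this is Φ{(0.02 − 1.96 × 0.0267)/0.0266} = Φ(−1.21) = 11.2%.

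| Control vs ROTEM (assumed) | Power, normal | Power, Fisher exact | n per arm for 80% (normal) |
|---|---|---|---|
| 1% vs 3% | 11.2% | 0.4% | 769 |
| 2% vs 6% | 18.6% | 4.3% | 376 |
| 5% vs 10% | 16.6% | 7.5% | 435 |
| 5% vs 15% | 41.5% | 28.5% | 141 |

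A significance test would be uninformative across this range. A count and an interval for each arm are what the trial can offer.

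**The case against.** The best defence is that serious thromboses are not lost. The complications list is open, the AE definition covers any untoward event whether or not related, and SAEs are followed to discharge and asked about again on day 30. By-arm counts could be tabulated from those records, and mortality would include fatal clots. This stands, and it rules out saying that thrombosis goes unrecorded.

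A reader might go further and infer that the comparison of benefit and harm is tilted towards ROTEM. The documents do not support that, for five reasons:

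- II.2 compares use of the concentrates. It states no expected difference or direction.
- Only infection and respiratory failure correspond to the transfusion harms in the background. Ventilation time, ICU stay and mortality are not specific to transfusion, and a serious thrombosis could worsen each of them.
- Control-arm providers follow institutional practice and their own judgement (III.4.a), and nothing bars them from the same products.
- No thrombotic risk is stated for any product. That link is general pharmacological reasoning.
- The notes to Figure 1 make cryoprecipitate an alternative to fibrinogen concentrate and attach conditions to rFVIIa. The flowchart was not available in the text reviewed, so how strongly the algorithm favours concentrates was not assessed.

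Low power is a fair limit on what the outcome can show, but not a reason to leave it out: 30-day mortality is compared with no stated power either.

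**Conclusion.** The point holds as a gap in definition, uniform ascertainment and planned comparison. The plan names no thromboembolic outcome and compares neither AEs nor SAEs by arm, while its algorithm notes list procoagulant products and one of them can replace a product counted in a main outcome. Neither the direction nor the size of any imbalance in thrombosis can be established from the documents, so no claim of bias towards ROTEM should be made.

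The conclusion rests on the text of II.2, III.5, IV and the Figure 1 notes, and on the premise that products given to promote clotting warrant a look for thrombosis. The RBC and FFP comparisons and the 55 per arm are unaffected. The change is worth making because a favourable report would otherwise lack a planned randomised comparison of this harm, and the remedy is cheap.

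**What to change.** Add to II.2 and III.5 a secondary safety outcome: symptomatic venous thromboembolism, myocardial infarction, stroke or other arterial thrombosis, from surgery to day 30. Take it from the chart during the stay and from the day-30 call already planned, with the same questions in both arms. Report this outcome and all SAEs by randomised arm as counts with confidence intervals.

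Events among patients who received PCC or rFVIIa should be listed descriptively and not compared. Receipt of these products follows randomisation and depends on how severely the patient bled, so such a comparison would be confounded by indication.

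The cost is protocol wording, one CRF item and a few questions on an existing call. No screening imaging, extra patients or change to treatment is needed. The drawback is a wide interval, so the plan should say in advance that the outcome is descriptive and that few or no events would not establish safety.

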If the case a subject withdraws from the study due to a serious adverse event the local IRB will be notified within 10 days.

Adverse Event definition

An AE is defined as any untoward medical occurrence in a patient or clinical investigational subject who has undergone an investigational procedure and that does not necessarily have to have a causal relationship with the study treatment. An AE can be any unfavorable or unintended sign, symptom, abnormal laboratory finding, or a temporal disease associated with the study procedure and monitoring, whether or not considered related to the procedure. Planned hospital admissions and/or surgical operations for an illness or disease that existed prior the subject was enrolled in a clinical study are considered part of the subject's medical history and are not considered AEs.

Serious Adverse Event

A SAE is any untoward medical occurrence that at any dose:

- Results in death
- Is life-threatening
- Results in persistent or significant disability/incapacity
- Requires in-subject hospitalization or prolongs hospitalization

Version: 1.0

- A congenital anomaly/birth defect

- Is another medically-significant event that, based upon appropriate medical judgment, may jeopardize the subject and require medical or surgical intervention to prevent one of the outcomes listed above.

V. Withdrawal criteria from the study

Reasons for premature discontinuation

According with the Declaration of Helsinki, participants have the right to withdraw from the study at any time for any reason. The Principal Investigator also has the right to remove a subject from the study. Reasons that a subject may be removed from the study include:

- An AE or SAE

- The request of the subject, his/her legal representative or caregiver, or investigator, for administrative or other reasons

- Non -compliance with medication, protocol violation, or unreliable behavior

- Any clinically significant abnormalities identified by the Principal Investigator according to his clinical judgment will be followed by appropriate tests and/or procedures until these abnormalities have subsided, returned to to clinically-acceptable levels, or can be attributed to causes other than the study procedure.

The principal Investigator may withdraw an enrolled and treated subject from the study for any of the following reasons:

- Occurrence of a serious or intolerable adverse event
- Emergence of a clinically-significant change in laboratory parameters.

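### Section V lets the investigator remove a treated patient from the study, not only from the assigned guidance, so postoperative secondary outcomes can be lost selectively

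*Combined protocol and SAP*

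**What the plan says.** Section V (Withdrawal criteria from the study) gives two lists of grounds.

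- The first opens with "Reasons that a subject may be removed from the study include". It names an AE or SAE, a request by the patient's side or by the investigator for administrative or other reasons, and non-compliance, protocol violation or unreliable conduct.
- The second opens with "The principal Investigator may withdraw an enrolled and treated subject from the study for any of the following reasons". It names "Occurrence of a serious or intolerable adverse event", "Emergence of a clinically-significant change in laboratory parameters", the patient's own request, a sufficiently serious protocol violation, and changes in condition that "render further treatment unreasonable or unsafe within the standards of clinical practice in the judgment of the Principal Investigator or treating physician".

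In both lists the patient leaves the study. Stopping the assigned transfusion guidance is not described as a separate step.

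Other relevant text:

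- Section IV counts as serious an event that "Requires in-subject hospitalization or prolongs hospitalization". AEs and SAEs are recorded from consent to discharge, and the IRB is notified when a subject withdraws because of an SAE.
- Section III.5 (Data collection) lists inpatient outcomes and a "Postoperative Day 30 phone call follow-up to assess serious adverse events and mortality".
- Section II.2 (Secondary objectives) includes "Compare the amount of all blood products transfused at 6, 12, and 24 hours postoperative", total in-hospital transfusion, ventilation time, ICU and hospital stay, infection and 30-day mortality.
- Section II.1 sets the primary objective on intraoperative red cells and plasma.

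**The concern.** Unsafe further treatment is a reason to stop a treatment strategy. It is not a reason to stop observing the patient. In this trial the ROTEM algorithm is applied to measurements taken during surgery, so after theatre little assigned guidance is left to stop. What remains is mostly the recording of hospital data and one telephone call. Ending that protects nobody and loses outcomes.

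The loss would not be random. The grounds overlap the outcomes: an event that lengthens the stay is an SAE, and length of stay is a secondary outcome. Patients withdrawn for an AE or a laboratory change plausibly go on to more transfusion, longer stays and more deaths, so the comparison would rest on a healthier remainder.

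The loss could also differ by arm. The decision is discretionary, and no text blinds the investigator to allocation. A breach of the ROTEM algorithm can occur in one arm only. The arm with more withdrawals would then look better than it is.

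**Working it through.** **Which outcomes are exposed.** The triggering event is normally already recorded, because AEs are captured from consent. What can go missing is whatever follows withdrawal.

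| Outcome | When it arises | Exposed? |
|---|---|---|
| Intraoperative red cells and plasma (primary) | Before the end of surgery | Only by withdrawal in theatre, or if withdrawn patients are dropped |
| Transfusion to 24 hours and total in hospital; ventilation; ICU and hospital stay; infection | After surgery | Yes |
| Day 30 SAEs and mortality | Day 30 call | Yes; the call is the only planned contact after discharge |

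**The plan's own figure.** Section III.3 gives 55 per arm for a difference of 3 units, SD 5, alpha 0.025 and 80% power. A two-sided two-sample t-test reproduces it: 54 per arm gives 79.9% and 55 gives 80.7%. The figure therefore contains no allowance for patients lost from the analysis.

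**Bound per patient.** With 55 per arm, k patients of unknown Day 30 status leave a range of k/55 in that arm's event rate:

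- k = 1: 1/55 = 1.8 points
- k = 3: 3/55 = 5.5 points
- k = 5: 5/55 = 9.1 points

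These are worst-case bounds, not expected biases.

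**Illustrated bias in a rate.** The documents give no withdrawal number, event rate or risk ratio, so all three are assumed. Let p be the true rate in the arm, w = k/55 the share withdrawn, and RR the later risk of withdrawn patients relative to the rest. Then p = r(1 − w) + r·RR·w, so the rate seen among those followed is r = p / [1 + (RR − 1)w].

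| True rate | k | RR | Seen |
|---|---|---|---|
| 10% | 3 | 2 | 0.10/1.0545 = 9.5% |
| 10% | 3 | 4 | 0.10/1.1636 = 8.6% |
| 10% | 5 | 2 | 0.10/1.0909 = 9.2% |
| 10% | 5 | 4 | 0.10/1.2727 = 7.9% |
| 5% | 3 | 2 | 0.05/1.0545 = 4.7% |
| 5% | 5 | 4 | 0.05/1.2727 = 3.9% |

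**Illustrated bias in a mean.** If withdrawn patients exceed the rest by D, the arm mean is understated by D·k/55.

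- D = 10 days of stay (assumed): 10 × 3/55 = 0.55 days; 10 × 5/55 = 0.91 days.
- D = 5 postoperative units (assumed): 5 × 3/55 = 0.27 units; 5 × 5/55 = 0.45 units.

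One-sided withdrawals carry these shifts into the difference between arms in full. Equal withdrawals of similar patients largely cancel.

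**Against sampling error.** At 10% in both arms the standard error of the difference is √(2 × 0.10 × 0.90/55) = 5.7 points, against shifts of 0.5 to 2.1 points. Borrowing the plan's SD of 5 for postoperative units, it is 5 × √(2/55) = 0.95 units, against 0.27 to 0.45.

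**The case against.** The strongest reply has four parts.

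- **The wording is permissive and generic.** Section V says the investigator may withdraw a patient, and nearby text speaks of medication and dose in a trial with no study drug. Both arms exist to detect and treat laboratory changes, so routine withdrawal for them would defeat the trial. This stands as a reason to expect low frequency. It does not change what the text permits.
- **Other text points towards continued recording.** Section III.5 covers patients in both groups without an exception, AEs are recorded to discharge, and Section V has clinically significant abnormalities followed until they settle or are explained. But none of this is a rule for a patient who has left the study, and following an abnormality is safety care, not collection of trial outcomes.
- **The sizes are assumed and small against sampling error.** This stands.
- **Absence is judged from the visible text.** A figure in the Section V list is not shown, and the numbering passes from VI to VIII. This is a fair caution.

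A reader might go further and infer that the primary comparison is biased or its type I error inflated. A stress calculation can suggest this: with no true effect, removing the 1, 3 or 5 highest of 55 values from one arm only raises the two-sided error from 2.5% to about 3.2%, 5.9% or 10.7%. The documents do not support that reading. The primary outcome is intraoperative and will usually be recorded before any withdrawal, and nothing says that withdrawn patients' earlier data are deleted or that the highest values in one arm would be the ones removed.

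**Conclusion.** The concern holds in a limited form. As written, Section V lets the investigator end a treated patient's participation on grounds related to outcome and, for some grounds, possibly to arm. No visible text keeps outcome collection going or requires analysis as randomised. The exposure is mainly in the postoperative secondary outcomes.

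The withdrawal rate is not given, so the size cannot be derived. What can be said without assumption about risk is that each patient with unknown Day 30 status leaves a 1.8-point range in an arm of 55. With 3 to 5 withdrawals in an arm and the assumed excess risks and excess amounts, the bias is modest and below one standard error of the comparison; it grows with the number withdrawn.

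A reader might also infer that such withdrawals are planned or expected to be common. The IRB notification sentence shows that they are foreseen, but nothing indicates how often. This is a cheap improvement, not a flaw that undermines the primary result.

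**What to change.** Reword Section V along these lines:

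> An AE, SAE, laboratory change, change in condition, protocol violation, non-compliance, unreliable behaviour or administrative reason may lead the investigator to stop the assigned transfusion guidance. It does not end study participation. All data listed in III.5 and the Day 30 call continue unless the patient withdraws consent.

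Add to the analysis text:

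> All randomised patients are analysed in their assigned group. The numbers stopping guidance or withdrawing consent, with reasons, are reported by group.

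The list must cover every investigator-initiated ground. If it stopped at safety reasons, protocol violation, non-compliance and administrative removal would still end follow-up, and these can differ by arm.

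The cost is a short amendment, with no new visits, tests or patients. The downside is that patients who stop the guidance remain in their group and slightly dilute the contrast.
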